4.1 Primary Objective

The Primary objective of this clinical study is to determine the relationships between BIS parameters, age, and depth of anesthesia in patients undergoing surgery under general anesthesia. It is also to improve the BIS™ Index performance in the elderly population.

For the primary objective, the following data gathered by the BIS™ system during general anesthesia, will be collected:

- EEG waveforms
- EMG
- BIS Number
- Total Power
- Anesthesia records

4.2 Secondary Objective

The secondary objective is to investigate BIS parameters, depth of anesthesia and physical and cognitive states in the study populations using the following tools:

- Mini Mental State Examination (MMSE)
- Mini Nutritional Assessment (MNA®-SF)
- Edmonton Frail Scale (EFS)

5 Study Design

This is a multicenter, non-invasive, interventional data collection study to improve the current BIS algorithm. Subjects undergoing a standard of care, elective non-ambulatory surgery under general anesthesia will be recruited. Eligible patients 18 years and older, will be informed of the study and invited to participate. Each eligible and consented subject will undergo the study assessments and procedures. The BIS™ sensors will be applied to the patient's forehead before anesthesia is administered. The BIS data will be collected throughout the surgery. The data recorded during the surgery will be provided to Medtronic.

It is planned to enroll up to 200 subjects from approximately 5 centers. It is anticipated that approximately 35% of enrolled patients will be between ages 18-64 years old, and approximately 65% of patients will be above the age of 65 years. In addition to basic demographic data collection, three assessments, the Mini Mental State Examination (MMSE), the Mini Nutritional Assessment (MNA®-SF), and the Edmonton Frail Scale (EFS) will be administered to each subject prior to surgery.

Study sites that enroll faster than others will be allowed to do so in order to maintain an adequate enrollment rate. To retain a good balance however, no more than 50% of total subjects expected to enroll at an individual study site.

6 Determination of Sample Size

Up to 200 subjects will be enrolled in the study, with 65% subjects over the age of 65 years. The sample size will provide adequate data information to assess the age impact for elder subjects with greater than 90% power to detect a distributional shift of BIS and MOAA/S scores between ages 18-64 and ≥ 65 years old (BIS 5-point, MOAA/S 0.5-point). Sample size calculations are based on the PASS software with a standard deviation of 10-point for BIS and 1.2 for MOAA/S. The sample size will also ensure high confidence to detect any rare safety events with an incidence as low as 2% (>98% confidence) or 1% (>86% confidence).

7 Statistical Methods

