5.1.1 Primary Objective(s)

To evaluate the relationships between BIS™ parameters, age, and depth of anesthesia in patients undergoing surgery under general anesthesia.

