The BIS technology converts raw EEG data acquired from the frontal cortex into a single number between 0 (isoelectric EEG) and 100 (fully awake). Given the numerous changes that occur in brain anatomy and physiology with typical aging, it is reasonable to assume that the EEG patterns of elderly patients and young patients under general anesthesia differ.

The purpose of the TIARA clinical study is to evaluate the relationships between BIS parameters, age, and depth of anesthesia in patients undergoing surgery under general anesthesia. In particular, to improve the BIS™ Index performance in the elderly population.

This statistical analysis plan (SAP) specifies the statistical methods to be implemented for the analysis of data used in the TIARA clinical study. It elaborates the statistical analyses specified in the CIP version 4, Dated November 9, 2020.

This document is created for internal use as a guideline for study Biostatistician and Statistical Programmer(s). Analysis results obtained from the analyses outlined in this document will be the basis of the Clinical Study Report (CSR) for this study.

As with any statistical analysis plan, the proposed methods and approaches to the data analysis should be considered as flexible to accommodate necessary changes. Changes to the plan may arise if the emerging picture suggests that deviations from the original plan would provide a more reliable and valid analysis of the data. The purpose of this plan is to provide general, and in some instances, specific guidelines from which the analysis will proceed. Nonetheless, sound statistical reasoning must substantiate deviations from these guidelines.

The planned analyses identified in this statistical analysis plan (SAP) may be included in regulatory submissions and/or future manuscripts. Additional exploratory analyses, not identified in this SAP, may be performed to support the clinical development program. Any post-hoc, or unplanned, analyses that are performed but not identified in this SAP will be clearly identified in the CSR.

4 Study Objectives

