7.3 Center Pooling

There are five participating centers in this study. Clinical procedure and data collection were executed under the same protocol. Every effort will be made to promote consistency in study execution at each study site.

Data poolability across sites will be assessed descriptively. Summary statistics of the primary outcomes (BIS, MOAA/S) will be presented by site, and statistical inferences may be provided for reference purposes. If the sites are found to be significantly heterogeneous, additional analyses will be conducted to further assess the differences between sites in baseline and procedural variables that might contribute to the differences.

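### The SAP still gives 200 subjects, about five centres and over 90% power; the current protocol plans up to 100 subjects from 2 centres and disclaims any power

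*SAP*

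**What the plan says.** **SAP.**
- The introduction ties the plan to an older protocol: "It elaborates the statistical analyses specified in the CIP version 4, Dated November 9, 2020".
- Section 4.1: "The Primary objective of this clinical study is to determine the relationships between BIS parameters, age, and depth of anesthesia".
- Section 5: "It is planned to enroll up to 200 subjects from approximately 5 centers". It also expects no single site to contribute more than half of the subjects.
- Section 6 repeats the 200, claims "greater than 90% power to detect a distributional shift of BIS and MOAA/S scores between ages 18-64" or older (shifts of 5 BIS points and 0.5 MOAA/S points), and adds: "Sample size calculations are based on the PASS software with a standard deviation of 10-point for BIS and 1.2 for MOAA/S". It then claims detection of rare safety events with an "incidence as low as 2% (>98% confidence) or 1% (>86% confidence").
- Section 7.3: "There are five participating centers in this study".
- Section 7.9, on changes to the planned analysis, is marked not applicable.

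**Protocol (CIP 5.1).**
- Section 5.1.1: "To evaluate the relationships between BIS™ parameters, age, and depth of anesthesia in patients undergoing surgery under general anesthesia".
- Section 6 plans up to 100 subjects from 2 centres and lets faster sites enrol more. It contains no 50% limit.
- Section 14.1 repeats the 100. It says the size was not derived from a hypothesis test and that the study, as a feasibility study, is not powered for a significant difference.
- The version history gives the reason for the change: the study had been written up as a validation study but was planned as a feasibility study.

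**The concern.** The two documents disagree in their current text on the maximum sample size, the number of centres, whether the study is powered, and the verb of the primary objective. The SAP says its results will be the basis of the clinical study report and may go into regulatory submissions and manuscripts.

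If section 6 is carried into the report, three things follow:
- The report would give twice the planned maximum sample size.
- A null comparison between age groups, which SAP 7.2.1 plans at P<0.05, could be read as informative because the study supposedly had more than 90% power.
- An absence of device-related events would be read as stronger evidence than 100 subjects can provide.

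**Working it through.** **1. Rare events.** Inputs: incidences of 2% and 1% (SAP 6), N = 200 (SAP 6) and N = 100 (CIP 14.1). Formula: P(at least one event) = 1 − (1 − p)^N.

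| N | p = 2% | p = 1% |
|---|---|---|
| 200 | 1 − 0.98^200 = 98.2% | 1 − 0.99^200 = 86.6% |
| 100 | 1 − 0.98^100 = 86.7% | 1 − 0.99^100 = 63.4% |

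The first row reproduces the SAP's figures, so this is evidently the formula used. With 100 subjects, the chance of seeing no event of 1% incidence is 36.6%, against 13.4% with 200. At 100, confidence of 98% and 86% is reached only for incidences of 1 − 0.02^(1/100) = 3.84% and 1 − 0.14^(1/100) = 1.95%. Nothing is assumed beyond the stated incidences and all N subjects being observed.

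**2. Power.** Inputs from the SAP: shifts of 5 and 0.5, SDs of 10 and 1.2 (section 6), a 35/65 age split (section 5) and a significance level of 0.05 (section 7.2.1). Standardised shifts: 5/10 = 0.500 and 0.5/1.2 = 0.417. The SAP does not state the test, sidedness or unit of analysis. I assume a two-sample t-test, one value per subject and no exclusions. Noncentrality = shift / (SD × √(1/n1 + 1/n2)); power is taken from the noncentral t distribution.

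| N (n1/n2) | Score | Noncentrality | Two-sided | One-sided |
|---|---|---|---|---|
| 200 (70/130) | BIS | 3.37 | 91.9% | 95.7% |
| 200 (70/130) | MOAA/S | 2.81 | 79.9% | 87.6% |
| 100 (35/65) | BIS | 2.38 | 65.6% | 76.5% |
| 100 (35/65) | MOAA/S | 1.99 | 50.3% | 62.9% |

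At 200 the BIS claim reproduces and the MOAA/S claim does not. For 90% two-sided power at a 35/65 split, about 187 subjects are needed for BIS and 268 for MOAA/S (one-sided: 152 and 219).

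MOAA/S does exceed 90% at N = 200 under conditions the SAP does not state. Examples are a one-sided test with equal groups (90.2%), or the mean of three readings with between-reading correlation r below about 0.62, if the SD is per reading.

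**3. Sensitivity to repeated readings.** If the SDs are per reading and m readings are averaged, the SD becomes SD × √((1 + (m − 1)r)/m). The documents give no r. With m = 3, N = 100, two-sided:

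| r | BIS | MOAA/S |
|---|---|---|
| 0.2 | 93% | 82% |
| 0.5 | 82% | 67% |
| 0.9 | 69% | 53% |

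With three readings, 90% needs r below about 0.30 (BIS) or 0.05 (MOAA/S). With five readings the limits are about 0.41 and 0.21.

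**4. Precision.** For BIS at one time stamp, the 95% confidence interval half-width for the age-group difference at N = 100 is 1.984 × 10 × √(1/35 + 1/65) = 1.984 × 10 × 0.2097 = 4.2 points. At N = 200 it is 2.9 points.

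**5. Site limit.** With two sites, a strict limit of 50% per site can be met only by an exactly even split. That conflicts with letting the faster site enrol more. If the sentence is read as an expectation only, there is no conflict.

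**The case against.** The strongest reply is that this is a version mismatch and not a calculation error. The SAP says openly that it follows CIP version 4, its rare-event figures and BIS power are right for 200 subjects, and the protocol says a SAP will be finalised before analysis, so an updated one may follow. Much of this stands as an explanation. It does not resolve the conflict: the SAP text under review contradicts the protocol in force, and its section on changes records none.

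Second, the 66% and 50% are not document figures. The primary analysis in SAP 7.2.1 uses logistic models with an age-by-BIS interaction, to which a t-test power does not apply. That is right. The figures are scenarios, and the count of three readings is a choice: the protocol schedules MOAA/S before induction, at three induction steps and at the start of maintenance, so up to five. The fix does not depend on them, because CIP 14.1 disclaims power whatever the test.

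Third, N = 100 is not fixed. CIP 14.1 allows sample size re-estimation and CIP 10.9 allows replacement of excluded subjects. But re-estimation only may happen, with no new number given, and 100 is the planned maximum.

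Fourth, enrolment is at consent, while device events are collected only from sensor placement to removal, so fewer than 100 may be exposed. This stands and belongs in any restated figure: with 90 exposed, the values are 84% and 60%.

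Finally, the verb of the objective and the site limit are minor; no analysis changes because of the verb.

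**Conclusion.** The concern holds. Without any modelling assumption, the SAP gives 200 subjects against a planned maximum of 100, about five centres against 2, and over 90% power where the protocol claims none. Rare-event confidence at 100 observed subjects is 86.7% (2% incidence) and 63.4% (1%), not over 98% and over 86%; fewer observed subjects would lower it further.

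The power figures at 100, about 66% for BIS and 50% for MOAA/S, rest on a two-sided 0.05 t-test, one value per subject, a 35/65 split and no exclusions. Averaging weakly correlated readings would raise them. The MOAA/S claim at 200 cannot be reproduced from what the SAP states (about 80%), but since the SAP does not describe its method, this is not a proven error. The site limit is a wording point that depends on how strictly it is read.

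This must be fixed before the SAP is used for the study report.

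**What to change.** - Change the protocol reference in the SAP introduction to CIP 5.1. Align section 4.1 with the protocol's objective (evaluate, not determine), sections 5 and 6 with up to 100 subjects, and sections 5 and 7.3 with 2 centres.
- Delete the power claim from section 6, in line with CIP 14.1. If any power statement is kept, give its test, sidedness, unit of analysis and N, and recompute it.
- Restate the rare-event confidence as 87% (2%) and 63% (1%), on condition that 100 subjects are observed with the devices in place. Since the protocol makes no such claim, deleting it would also serve.
- Reconcile the 50%-per-site sentence with a two-site design.
- Optionally, give the precision of the BIS age-group comparison at one time stamp: half-width about 4.2 points at N = 100 (SD 10, 35/65, no exclusions).

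The cost is SAP wording only. The stated figures become less favourable. No extra patients, procedures or protocol amendment are needed.

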7.2.1 Statistical Method

Descriptive statistics will be used to summarize study outcomes. Subjects with valid recorded data from the study device (EEG signals) and a completed eCRF will be included in the primary analysis.

The relationships between BIS parameters, age, physical and cognitive state, and depth of anesthesia in patients undergoing surgery under general anesthesia will be assessed. Also, the relationship between BIS and MOAA/S will be examined by subjects under 65 and by subjects over 65 years old. Pearson's correlation or Spearman's rank correlation will be calculated as appropriate. Continuous variables will be evaluated using analysis of variance (ANOVA) or nonlinear E_{max} model, and categorical variables will be evaluated using the chi-square or Fisher's exact test, as well as multivariate logistic regression with age as an explanatory factor. A P-value of less than 0.05 is considered statistically significant unless otherwise specified.

Specifically, for the primary objective, a polytomous logistic regression model will be employed to assess the relationship between the MOAA/S scale and the BIS score/age groups (18-64 vs. 65+). The interaction between age and BIS score will be included. Another dichotomous logistic regression model will be utilized as well, when the MOAA/S scale is classified as responsive (scale of 2, 3, 4, and 5) and non-responsive (scale of 0 and 1).

The BIS scores at various time stamps (e.g., first response, extubation, etc) will be compared between the two age groups.

A simplified Sigmoid E_{max} model will also be used to analyze the relationship between the BIS™ index and loss of responsiveness through the probability of response curves. The values of BIS™ at which 50% (BIS_{50}) and 95% (BIS_{95}) of subjects are unresponsive, and their 95% confidential intervals will be derived. The systematic variance between groups will be evaluated.

The model is as follows:

$$P = \frac{e^{a+bX}}{1 + e^{a+bX}}$$

where P is the probability of "unresponsive", X is the explanatory variable (BIS™ value or anesthetic agent concentration on the log scale), and a & b are model parameters.

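### SAP section 6 claims more than 90% power for both scores, but its stated inputs support that for BIS only; for MOAA/S a plain two-sided test gives about 80%

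*SAP*

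**What the plan says.** SAP section 6 (Determination of Sample Size) attaches one figure, greater than 90%, to two scores. The claim is worded as "power to detect a distributional shift of BIS and MOAA/S scores between ages 18-64 and ≥ 65 years old (BIS 5-point, MOAA/S 0.5-point"). The spread is given in the next sentence: "Sample size calculations are based on the PASS software with a standard deviation of 10-point for BIS and 1.2 for MOAA/S". Enrolment is set by "Up to 200 subjects will be enrolled in the study, with 65% subjects over the age of 65 years", and SAP section 5 describes the age mix: "approximately 35% of enrolled patients will be between ages 18-64 years old, and approximately 65% of patients will be above the age of 65 years".

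Section 6 does not name a test, a significance level, one or two sides, or how many MOAA/S scores each subject contributes. The only significance level is the general rule in SAP 7.2.1: "A P-value of less than 0.05 is considered statistically significant unless otherwise specified". SAP 7.4 makes no multiplicity adjustment, so alpha is not divided between the scores.

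The SAP's introduction says that it elaborates CIP version 4. The current protocol, CIP 5.1, plans up to 100 subjects from 2 centers. Its section 14.1 describes a feasibility study whose size is not meant to detect a significant difference, and its version history records both changes.

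**The concern.** The two shifts differ in standardised size: 5/10 = 0.50 SD for BIS and 0.5/1.2 = 0.417 SD for MOAA/S. The same subjects in the same split cannot give similar power for both. If the figure only just clears 90% for BIS, it must fall short for MOAA/S under the same test.

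What is at stake is how the number is reused. The SAP says that its results will be the basis of the clinical study report and may go into submissions or manuscripts. If the joint sentence were quoted as the design power, a reader would put the chance of missing a 0.5-point MOAA/S shift at under 10%, when the stated inputs imply about 20% at 200 subjects. A revision that changed only N would keep one figure for two scores that need separate figures.

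**Working it through.** **Inputs.** N = 200 and 65% older (SAP 6), so n1 = 0.35 × 200 = 70 and n2 = 0.65 × 200 = 130. BIS: shift 5, SD 10. MOAA/S: shift 0.5, SD 1.2 (SAP 6). Alpha 0.05 (SAP 7.2.1). Assumed, because not stated: two-sided test, one score per subject.

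**Formula.** Two-sample t-test with df = n1 + n2 − 2 = 198. Noncentrality = (shift/SD) × √(n1·n2/(n1 + n2)), where √(70 × 130/200) = 6.745. Power is the probability that a noncentral t exceeds the critical value in absolute size: 1.972 two-sided, or 1.653 for the upper tail one-sided. For Mann-Whitney under normality, both group sizes are multiplied by the asymptotic relative efficiency of 0.955.

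**BIS, the plan's own figure first.** Noncentrality = 0.50 × 6.745 = 3.37. Two-sided power is 91.9% (t) and 90.6% (Mann-Whitney). The claim of more than 90% reproduces.

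**The other figures in the same paragraph.** For rare safety events, 1 − 0.98^200 = 98.2% and 1 − 0.99^200 = 86.6%. Both match section 6, which confirms that N = 200 is the right base.

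**MOAA/S.** Noncentrality = 0.417 × 6.745 = 2.81.

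| Setting | t-test | Mann-Whitney (normal) |
|---|---|---|
| 70 vs 130, two-sided | 79.9% | 78.0% |
| 70 vs 130, one-sided | 87.6% | 86.3% |
| 100 vs 100, two-sided | 83.4% | 81.7% |
| 100 vs 100, one-sided | 90.2% | 89.0% |

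At the stated split no cell reaches 90%. The only cell that does needs a one-sided test and equal groups, and equal groups contradict the planned 35/65.

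**What 90% would need** (two-sided t, 35/65, changing one input at a time): a shift of about 0.58 points, or an SD of about 1.04, or about 268 subjects.

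**Routes above 90% that add an unstated assumption.**
- Mann-Whitney with a non-normal shape at 70 vs 130: logistic (efficiency 1.097) gives 83.4% two-sided and 90.1% one-sided; double exponential (efficiency 1.5) gives 92.9% two-sided.
- Mann-Whitney on 0–5 scores that pile up at an end of the scale: simulation with SD 1.2 in both groups and a 0.5 shift gave 92.8% for group means of 0.9 and 1.4, and about 99% for 0.5 and 1.0. For central means it gave about 80%. A different construction, rounding and clipping normal scores to 0–5, gave 72–76%, so the simulated value depends on the assumed score distribution.
- Three scores averaged per subject: the SD becomes 1.2 × √((1 + 2ρ)/3), where ρ is the within-subject correlation. At ρ = 0.6 this is 1.03 and power is 90.4%; at ρ = 0.7 it is 1.07 and power is 87.8%.

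**Current N.** At 35 vs 65, √(35 × 65/100) = 4.770 and df = 98. BIS: noncentrality 2.38, power 65.6%. MOAA/S: noncentrality 1.99, power 50.3% (two-sided t).

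**The case against.** A reader might infer that the MOAA/S figure was simply wrong when it was written. The documents do not go that far. Section 6 is silent on test, sidedness and scores per subject, so two-sidedness and one score per subject are assumptions of this check. Its phrase about a distributional shift suggests a rank test, and MOAA/S is a bounded 0–5 ordinal scale (CIP Appendix A). CIP 10.6.3 has it scored before induction and at each of three propofol steps, and the CIP synopsis expects a score of 0 to be confirmed at the start of maintenance. Pile-up at an end of the scale and repeated scores are therefore both plausible, and either can lift power above 90%. That stands: what was entered in PASS cannot be recovered. It does not rescue the figure, because section 6 gives only a shift and an SD and mentions neither feature. The tests named in SAP 7.2.1 (ANOVA, chi-square) are also non-directional, which makes a two-sided reading the natural one.

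A second objection is that CIP 5.1 has overtaken the sentence. It has dropped the power claim and halved N, so the gap between 80% and 90% at 200 subjects no longer decides anything about the study. That also stands and limits the consequence. The SAP supplied still carries the sentence, however, and now conflicts with CIP 5.1.

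A third tempting inference is that the primary analysis has only about 80% power. The documents do not support it. MOAA/S is the outcome of the primary-objective models, but these are polytomous and dichotomous logistic regressions with an age-by-BIS interaction (SAP 7.2.1). A two-group shift test does not measure what they can show.

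**Conclusion.** The joint claim is not supported by the inputs stated beside it. At 70 vs 130 with two-sided alpha 0.05 and one score per subject, the claim holds for BIS (91.9% t, 90.6% Mann-Whitney) and falls 10 to 12 points short for MOAA/S (79.9% and 78.0%). A one-sided test narrows the gap to 2.4 points by t-test and 3.7 by Mann-Whitney without closing it. This rests on reading the stated SD as the SD of a single score per subject and on a t-test or normal-theory rank test. Under the unstated assumptions listed above, more than 90% is attainable, so the finding is that the figure is unsupported, not that it is proved false.

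This is a correction to the SAP's text. It is separate from the mismatch in N, because the shortfall is present at the SAP's own 200 subjects, but it is best resolved together with that mismatch. It does not show that the study needs more subjects.

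**What to change.** - Remove the joint power claim for BIS and MOAA/S from SAP section 6, and do not carry it into the clinical study report.
- Align section 6 with CIP 5.1: up to 100 subjects, feasibility aim, not powered for a significant difference.
- If any power or precision figure is kept, give it separately for each score at the current N, naming test, sidedness, split and scores per subject. At 35 vs 65 with a two-sided t-test and the SAP's shifts and SDs, this is about 66% for BIS and about 50% for MOAA/S.
- If the 200-subject design is cited as history, state more than 90% for BIS only and about 80% for MOAA/S. If the sponsor's PASS record shows a different test or repeated scores, state those inputs so that the figure can be reproduced.

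The cost is a few sentences of SAP wording and a less favourable stated figure. No extra subjects are needed and study conduct does not change.
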